5.6 Study Day 140 ± 7 (Visit 7) or Early Termination Visit

On Study Day 140 ± 7 each Subject will report to the Principal Investigator's office for the following procedures:

- Measure vital signs (blood pressure, pulse, respiration rate, and oral temperature);
- Assess any change in concomitant medication;
- Complete pain scale;
- Perform physical examination including review of systems and breast and gynecologic exam;
- Vulvoscopy including photograph(s) of the vulva, vestibule and vagina region and pain scale/Q-tip testing;
- Complete visual scale;
- Collect medication and calculate compliance;
- Collect diaries;
- Assess adverse events.

If a Subject terminates study participation or is withdrawn from the study by the Principal Investigator before visit 7, the Subject should return to the Principal Investigator's office as soon as possible for the following procedures:

- Measure vital signs (blood pressure, pulse, respiration rate, and oral temperature);
- Assess any change in concomitant medication;
- Complete pain scale;
- Assess any change in concomitant medication since screening visit;
- Perform physical examination including review of systems and breast and gynecologic exam;
- Vulvoscopy including photograph(s) of the vulva, vestibule and vagina region and pain scale/Q-tip testing;
- Complete visual scale;
- Collect medication and calculate compliance;
- Collect diaries;
- Assess adverse events.

6 Adverse Event Assessment

6.1 Adverse Events

An adverse event (AE) is any undesirable sign, symptom, medical condition, or laboratory abnormality occurring after the Subject has taken the first dose of study medication, whether the event is considered study medication-related or not. Medical conditions or diseases present before starting study medication are only considered adverse events if they worsen after starting study medication. The Principal Investigator will follow all Subjects who experience an adverse event until the Subject's medical condition returns to normal or until a clinically satisfactory resolution is obtained.

Adverse events are classified in several ways: as either serious or non-serious, and either expected or unexpected. Serious adverse events (SAEs) include those that result in death, are life threatening, require inpatient hospitalization or result in prolongation of an existing hospitalization, result in persistent or significant disability or incapacity, require medical or surgical intervention to prevent one of the outcomes described above, are congenital anomalies or birth defects, or are medically important events or reactions (see Section 7.2). Non-serious adverse events are those adverse events that do not meet the above criteria for serious adverse events. Expected adverse events are those events that have been previously observed and are described in the current prescribing information for the study medication. Unexpected adverse events are those events that are not listed in the prescribing information, or are not consistent with the specificity or severity described in the current prescribing information.

Any abnormality that, in the judgment of the Principal Investigator or a physician identified on Form FDA 1572, impacts the health, safety, or well-being of the study participant such that immediate follow-up (e.g., additional testing or treatment intervention) is warranted is considered a clinically significant abnormality. A determination of clinical significance is independent of whether or not the abnormality is considered causally related to the use of the study medication.

6.2 Serious Adverse Events

A SAE is defined by federal regulation as any AE that results in any of the following outcomes:

1. Death
2. Life threatening (Subject is at risk of death at the time the event occurs)
3. Persistent/significant disability or incapacity (substantial disruption of a person's ability to conduct normal life functions)
4. Inpatient hospitalization or prolongation of an existing hospitalization.

5. Congenital anomaly or birth defect.

Additionally, important medical events that may not result in death, be life threatening, or require hospitalization may be considered a SAE when, based upon appropriate medical judgment, they may jeopardize the Subject and may require medical or surgical intervention to prevent one of the outcomes listed in this definition.

Any SAE occurring in a Subject after providing informed consent and until 30 days after completing the study must be reported to the Aspire IRB. The reporting period may be extended if there is a strong suspicion of a study medication reaction. Reports of overdose must be monitored and reported as an SAE.

6.3 Adverse Event Reporting

All adverse events, whether volunteered by the Subject, discovered during general questioning by the Principal investigator, or detected through a physical examination or other means, will be recorded in the clinic chart (source document) and on the Adverse Events CFR. Each description of an adverse event will include:

1. Duration: start and stop dates
2. Expectedness
3. Severity: events will be classified as either *mild* (causing no limitation in normal activities), *moderate* (causing some limitation in normal activities), or *severe* (causing significant limitation in or the inability to perform normal activities)
4. Action taken
5. Relationship to the study medication: not related, possibly related, or probably related
6. Outcome: resolved, continuing requiring no treatment, continuing requiring treatment, hospitalization, or death

Whenever possible, adverse events causing premature study discontinuation should be followed to resolution.

All SAEs occurring during the study and up to 28 days after the Subject completes the study (visit on Day 84 or earlier) *must be reported to the Aspire IRB within 1 week of learning of the event with the exception of death which must be reported within 24 hours*. Additionally, the Principal investigator must provide any other AE notification required by the IRB. Each SAE is to be recorded on a SAE worksheet along with follow-up records. Examples of follow-up records may include photocopies of hospital records, consultation reports, autopsy findings, laboratory reports, and a summary of the outcome of the reaction.

6.4 Risks

The risks to Subjects in this study are those associated with in the package insert for ospemifene: hot flashes, vaginal discharge, muscle spasms and increased sweating. Less common but serious side effects include stroke, blood clots and cancer of the lining of the uterus.

7. Study Medication and Accountability

The Principal Investigator is responsible for study medication at the investigational site, including storage, accountability, record keeping, and reconciliation.

7.1 Study Medication

Ospemifene (Osphena[®]) 60 mg tablets will be provided by Shionogi Pharmaceuticals, in sufficient quantity to dose all Subjects.

The ospemifene tablets provided for this study will be taken from commercial drug supply.

7.2 Study Medication Blinding

This is an open-label (unblinded) study and no blinding of study medication is required.

7.3 Study Medication Labeling

Each envelope of medication provided to each Subject will be marked as to subject (initials and subject number), visit number and date of dispensing.

7.4 Study Medication Storage

Ospemifene will be stored in a cool, dry place. The study medication shall be stored in a securely locked, substantially constructed enclosure to which access is limited. The Principal Investigator shall take adequate precautions, including locked storage, to prevent theft or diversion of the study medication, consistent with CFR Title 21, part 312.69.

7.5 Study Medication Handling

Study medication will be shipped to the investigational site after the granting agency (Shionogi Pharmaceuticals) has received the required study documents in accordance with regulatory requirements.

All study medication is to be administered in accordance with the protocol and only to enrolled Subjects. Only authorized personnel may supply the study medication to each Subject.

7.6 Study Medication Accountability

All study medications will be Subject to inventory upon receipt, and stored in accordance with Section 8.4. Applicable regulatory requirements for this study will be enforced by the Principal Investigator or designated site personnel through the study. The Principal Investigator (or designee) will document the date, Subject identification, and lot number used each time drug is dispensed for Subject use.

Throughout the study, the Principal Investigator will maintain an accounting of all study medication. The Principal Investigator must not destroy any unused study medication. The Principal Investigator will return all unopened study medication and a copy of the completed drug disposition form to Shionogi Pharmaceuticals.

8. Statistical Methods

8.1 Determination of Sample Size

The sample size of 10 menopausal Subjects was chosen for this study based on this being a pilot study and this sample size will be sufficient to prospectively document visible changes to the vulva, vestibule and vagina in post-menopausal women with VVA and dyspareunia. There will be a total of 6 photographic sessions of the vulva, vestibule and vagina over the 20 weeks of the study. The photograph(s) at baseline (vulvoscopy session 0) will be compared to photographs at 4 weeks (vulvoscopy session 1), 8 weeks (vulvoscopy session 2), 12 weeks (vulvoscopy session 3), 16 weeks (vulvoscopy session 4) and 20 weeks (vulvoscopy session 5).

8.2 Photographic Data

Changes to the vulva, vestibule and vagina will be examined prospectively by comparing photographs of post-menopausal women with VVA and dyspareunia at 4 weeks, 8 weeks, 12 weeks, 16 weeks and 20 weeks while on treatment with 60 mg ospemifene. The proportion of subjects with improvement will be tabulated by scheduled visit.

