2. TRIAL OBJECTIVE

The primary objective of this study is to prospectively document, using vulvoscopy with detailed photography, the visible changes to the vulva, vestibule and vaginal region in post-menopausal women with dyspareunia taking 60 mg daily ospemifene for twenty weeks at 6 timepoints: baseline, 4 weeks, 8 weeks, 12 weeks, 16 weeks and 20 weeks.

Secondary objectives include changes in pain as noted on the pain scale (appendix 2) and the q-tip test, in the vestibule on visual scale (appendix 3) by the clinician and sexual function by subject diary (appendix 4).

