3.4 Rationale for Study Design and Subject Selection

Currently there have been limited prospective studies using vulvoscopy with detailed photography demonstrating visible changes to the vulva, vestibule and vagina following oral administration of 60 mg ospemifene in post-menopausal women with VVA and dyspareunia. Information regarding visible changes to the vulva, vestibule and vagina may be very important to the patient and to the health care provider to best understand the beneficial effects of ospemifene and to ensure patient compliance with treatment.

This study is being conducted in an unblinded fashion because the primary endpoint is a collection of photographs. All subjects will receive the same active drug at the same dosage.

4. Selection and Withdrawal of Subjects

The study population will include menopausal females with vulvar vaginal atrophy (VVA) causing dyspareunia.

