8.3 Patient Reported Outcomes

Mean pain score will be summarized at each scheduled visit. Subjects will also be categorized at each visit as having more pain, the same pain, or less pain compared to baseline.

Mean scores will be summarized for each item of the visual scale at each scheduled visit. Subjects will also be categorized at each visit as worsened, unchanged, or improved compared to baseline for each item of the visual scale at each scheduled visit.

For each subject, the proportion of total sexual events with a 'yes' response since the last scheduled visit will be calculated for each diary question at each scheduled visit.

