AN OPEN-LABEL PILOT PROSPECTIVE VULVOSCOPY WITH PHOTOGRAPHY  
STUDY OF THE VISIBLE CHANGES IN THE VULVA, VESTIBULE AND VAGINA PRE-  
AND POST- TWENTY WEEKS OF DAILY ADMINISTRATION OF 60 MG  
OSPEMIFENE IN POST-MENOPAUSAL WOMEN WITH DYSPAREUNIA FROM  
VULVAR VAGINAL ATROPHY

NCT 02784613  
April 4, 2016

Each subject's baseline and end of the study vulvoscopic photographs were subsequently assessed using a four-point rating scale, the vulvoscopic genital tissue appearance (VGTA) scale. The VGTA scale has not been validated. This scale assesses ten different parameters of the appearance of the genital tissue including loss of labia majora, loss of labia minora, decreased size of glans clitoridis, prominence of urethral meatus, stenosis of introitus, vestibular pallor, vestibular erythema, loss of vestibular moisture, loss of vaginal rugae, and loss of prominence of the anterior vaginal wall (Table 2). Each subject could score between 0 and 30 total points on the VGTA at each visit. A higher score of the VGTA scale was considered consistent with a worse vulvoscopic genital tissue appearance.

Baseline physical examination was performed as part of the screening. The physical exam included performance of a cotton-tipped swab testing where the examiner applied gentle pressure at each location of the vestibule: 1:00, 3:00, 5:00, 6:00, 7:00, 9:00, and 11:00 o'clock. The subject was asked to rate her pain on a scale from 0 to 3. Aggregate pain scores at baseline and study end were compared using the Wilcoxon signed-rank test.

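### The by-visit summary of the primary photographic outcome counts only women who improved, so it cannot separate net benefit from reading noise or show photographic worsening at that visit.

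*Protocol*

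**What the plan says.** Protocol Section 2 states the aim without a direction: "The primary objective of this study is to prospectively document, using vulvoscopy with detailed photography, the visible changes to the vulva, vestibule and vaginal region". Section 3.4 says that "the primary endpoint is a collection of photographs". All women receive the same drug, so there is no comparison group.

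Section 8.2 plans to compare the photographs at weeks 4, 8, 12, 16 and 20, and gives one summary: "The proportion of subjects with improvement will be tabulated by scheduled visit". It does not say what counts as improvement.

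Section 8.3 treats the secondary outcomes differently. For pain: "Subjects will also be categorized at each visit as having more pain, the same pain, or less pain compared to baseline". For the clinician's visual scale: "Subjects will also be categorized at each visit as worsened, unchanged, or improved compared to baseline for each item of the visual scale".

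The SAP introduces the VGTA scale for the photographs, with ten four-point parameters and higher scores meaning worse appearance. It says that "Each subject could score between 0 and 30 total points on the VGTA at each visit", but describes scoring of the baseline and end-of-study photographs only. It compares pre- and post-treatment scores by a two-tailed Wilcoxon signed-rank test. It mentions neither the proportion improved nor any photographic result for weeks 4 to 16. It states that the scale is not validated.

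**The concern.** A proportion improved does not have a null value of zero. If each photograph is read with some error and the tissue has not changed, some women will appear better and about as many will appear worse. A table that keeps only the first group shows a favourable figure whether or not anything happened.

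A randomised trial would supply the missing benchmark from its control arm. Here the only internal benchmark is the number of women who moved the other way, and Section 8.2 leaves that number out. Four of ten women improved is a signal if none worsened, and is what noise looks like if four worsened. The planned table prints the same entry for both. It also reports less than the objective asks for, since the objective is visible change in either direction.

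**Working it through.** **Inputs from the documents.** Ten women (Protocol 8.1). Ten VGTA items scored 0–3, total 0–30, higher is worse (SAP). Improved share by visit (Protocol 8.2). The sample size has no alpha, power or expected rate behind it, so there is no planned figure to reproduce. Neither document gives a reading-error, agreement or tie rate. Every rate below is therefore an assumption.

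**Step 1: general result.** With no true change and symmetric error, P(improved) = P(worsened). The three categories sum to 1, so P(improved) = (1 − P(tie))/2, where a tie is any pair of readings classed as unchanged.

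| Assumed tie rate | P(improved) from noise alone |
|---|---|
| 0% | 50% |
| 20% | 40% |
| 33% | 33% |
| 50% | 25% |
| 80% | 10% |
| 90% | 5% |

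**Step 2: tie rate from a misread rate.** Suppose each item reading is off by one point with probability q, equally often up or down, independently at the two visits. For one item without floor or ceiling, P(tie) = (1 − q)² + 2(q/2)². At q = 0.10 this is 0.81 + 0.005 = 0.815, so P(improved) = (1 − 0.815)/2 = 9%. For the ten-item total, the item difference is convolved ten times.

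| Rule for improved | q = 0.10 | q = 0.20 | q = 0.30 |
|---|---|---|---|
| Single item falls | 9% | 17% | 23% |
| Total falls by at least 1 | 35% | 40% | 42% |
| Total falls by at least 1, readings held within 0–3, true scores uniform on 0–3 | 32% | 38% | 40% |
| Total falls by at least 2 | 13% | 22% | 27% |
| Total falls by at least 3 | 4% | 10% | 15% |

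Rows other than the third have no floor or ceiling. At q = 0.05, a single item gives 5% and any fall in the total gives 27%. A rule that calls a woman improved if any one of ten items falls gives 39% at q = 0.05 and 85% at q = 0.20. That rule lies outside the formula in Step 1, because a woman can then be both improved and worsened.

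**Step 3: what ten women would show.** If P(improved) were one third, the expected count is 10 × 1/3 = 3.3, and the binomial chance of 5 or more improved at a given visit is 21%. At 40% that chance is 37%. An observed 3 of 10 has an exact 95% interval of 7% to 65%.

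**Step 4: what the other columns add.** With 4 improved, 6 unchanged and 0 worsened, the net difference is 4 − 0 = 4 women. With 4 improved, 2 unchanged and 4 worsened, it is 4 − 4 = 0. Symmetric noise has an expected net difference of zero at any tie rate, so the net figure needs no assumption about q.

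**Step 5: what the SAP test covers.** For ten untied differences the two-sided signed-rank test rejects when the smaller rank sum is 8 or less, at exact level 0.0488. Symmetric noise is thus controlled for baseline against week 20. The SAP has no counterpart for weeks 4, 8, 12 and 16.

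**The case against.** The best defence is that worsening is counted elsewhere. The signed-rank test sets worsened photographs against improved ones at week 20. The visual scale is categorised three ways at every visit, and its pallor, redness and dryness overlap VGTA pallor, erythema and moisture. Adverse events are collected throughout. This stands, and it rules out two readings that a reader might infer: that the study never counts worsening, or that it cannot show harm. The gap is confined to the photographic by-visit table. The visual scale does not fill that gap, because it is a separate five-item clinician rating and not a reading of the photographs.

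It is also fair that no document supports a fixed noise rate. A reader might infer that about a third of women would look improved at every visit. That needs a tie rate near one third, and the figures of 32% to 40% need the VGTA total to be used at weeks 4 to 16, any one-point fall to count, readings held within 0–3 and uniform true scores. The documents state none of these as the rule for the by-visit table, and a two-point threshold or a single item gives much less.

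Finally, this is a descriptive pilot: "The sample size of 10 menopausal Subjects was chosen for this study based on this being a pilot study". Section 8.2 attaches no test or success criterion to the proportion, and the share not improved follows by subtraction. But subtraction cannot split unchanged from worsened, which is the split that matters. With ten women, each reclassified woman moves the proportion by 10 percentage points.

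**Conclusion.** The point holds for the photographic by-visit table. Section 8.2 specifies a one-directional summary of the primary outcome in a single-arm study, while the next section uses the balanced format for secondary outcomes. The improved-only table therefore cannot separate net benefit from symmetric reading noise, and it cannot show photographic worsening.

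The size of the noise-only share is unknown. For a single score it is roughly 5% to 50%, depending on the undefined rule and the unstated error rate; strict thresholds can take it slightly lower and an any-item rule well above. The conclusion needs only that error is symmetric and that some readings do not tie.

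The SAP's two-tailed test offsets the problem at week 20. At weeks 4 to 16 the improved share is the only photographic summary planned. A reader should not conclude that the week-20 comparison fails on this ground. Nor does the finding address directional bias from a reader who sees the photographs in date order, which is a separate matter.

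**What to change.** In Protocol Section 8.2 and in the SAP:

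- State the rule for improvement, for example any fall in the photographic score from baseline, with the mirror rule for worsening.
- Tabulate improved, unchanged and worsened at each scheduled visit, with the net difference (improved minus worsened).
- Quote the improved share only with the worsened share beside it.

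No by-visit significance test is needed. A sign test at each of five visits would add correlated tests to a ten-woman descriptive study. With no ties, each would need a split of 9 to 1 or better (8 to 2 gives two-sided p = 0.11; 9 to 1 gives 0.02), and at week 20 it would overlap the signed-rank test.

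The cost is a few lines of text and extra table columns, with no new visits or photographs. The headline may look less favourable. If the VGTA is used for weeks 4 to 16, the existing reader must score those photographs too, but Section 8.2 already requires them to be compared.

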8.3 Patient Reported Outcomes

Mean pain score will be summarized at each scheduled visit. Subjects will also be categorized at each visit as having more pain, the same pain, or less pain compared to baseline.

Mean scores will be summarized for each item of the visual scale at each scheduled visit. Subjects will also be categorized at each visit as worsened, unchanged, or improved compared to baseline for each item of the visual scale at each scheduled visit.

For each subject, the proportion of total sexual events with a 'yes' response since the last scheduled visit will be calculated for each diary question at each scheduled visit.

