Appendix 4: Diary

Initials _____ Number _____ Date _____

Please complete after each sexual event, answering all questions.

If you experienced dryness before were you less dry? Yes No N/A

Did you use lubricant during this activity? Yes No

Did you experience pain/discomfort during foreplay? Yes No N/A

Did you experience pain during masturbation? Yes No N/A

Did you experience pain during oral sex? Yes No N/A

Did you experience pain during intercourse? Yes No N/A

Did you stop early because of discomfort? Yes No

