Baseline sexual function diary data concerning dryness and sexual pain were collected. The questions of the sexual function diary have not been validated. For 4 weeks prior to each study visit, subjects recorded yes or no answers to the following questions for each sexual encounter: 1) did the subject experience dryness before and were you now less dry, 2) did the subject use lubricant during this sexual activity, 3) did the subject experience pain/discomfort during foreplay? 4) did the subject experience pain during masturbation, 5) did the subject experience pain during oral sex, 6) did the subject experience pain during intercourse, and 7) did the subject stop early because of discomfort. Diaries were collected and new ones administered at each subsequent visit. The number of total sexual events, as well as percentage of total sexual events with pain or lubrication difficulty was compared for diaries collected at week 0 and week 20 using the Wilcoxon signed-rank test.

At the completion of the study, the photographs were sorted by subject number and date of exam and assessed by the principal investigator, a sexual medicine physician, who had not examined any of the women in person. He assigned scores to the photographs using pre-determined Likert scales for the 10 parameters of VGTA scale (Table 2). Differences in pre-and post-treatment scores were compared using Wilcoxon signed-rank test for non-parametric matched pairs. All tests of significance were 2-tailed with  $p < 0.05$  considered significant. All analyses were performed in Stata®, version 13.

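### Protocol 8.3 divides every diary item by all sexual events although five of seven items allow N/A, so a pain item moves with activity mix; separately, the SAP's week-0 diary has no place in the protocol schedule.

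*Protocol*

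**What the plan says.** **Denominator.** Protocol 8.3 defines the diary statistic as "For each subject, the proportion of total sexual events with a" yes answer, and extends it to the whole form: "response since the last scheduled visit will be calculated for each diary question at each scheduled visit". It plans no test. The SAP's diary paragraph also uses total events, comparing week 0 with week 20 by the Wilcoxon signed-rank test: "percentage of total sexual events with pain or lubrication difficulty was compared".

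**Response options.** The form in Appendix 4 is filled in once per event: "Please complete after each sexual event, answering all questions". Five items carry N/A: the dryness item ("If you experienced dryness before were you less dry? Yes No N/A") and pain in foreplay, masturbation, oral sex and intercourse (for example "Did you experience pain during intercourse? Yes No N/A"). Lubricant use and stopping early are yes/no only. Neither document says how N/A is counted, and the SAP describes the answers as yes or no.

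**Baseline and recording period.** The SAP says "Baseline sexual function diary data concerning dryness and sexual pain were collected", and gives the period as follows: "For 4 weeks prior to each study visit, subjects recorded yes or no answers". In the protocol, Section 5.2 lists no diary at screening, Section 5.4 first hands out diaries on Day 0, and Section 5.5 and Appendix 1 first collect them at Visit 3.

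**The concern.** If N/A stays in the denominator, an event without intercourse counts as an event without intercourse pain. The per-item percentage then mixes two things: how often intercourse hurts, and how often it is attempted. In women enrolled for dyspareunia both may change on treatment, in either direction. A report could show less pain because intercourse was avoided, or no benefit because it was resumed. The SAP's comparison of total event counts would not reveal a shift between activities.

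The dryness item behaves differently. Yes is the favourable answer there, and N/A depends on whether there was earlier dryness, so the percentage mixes improvement with how often the question applied.

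Two SAP terms add to the uncertainty. Its pain percentage may be per item or any pain in an event. Its lubrication-difficulty category matches no question on the form, which asks about being less dry and about lubricant use. Two analysts could report different results from the same diaries.

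The week-0 conflict is a separate matter. It decides whether the SAP's diary comparison has a pre-treatment side at all.

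**Working it through.** The documents state no figure to reproduce, and give no activity shares, pain risks or event rates. All inputs below are assumed unless a source is named.

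**1. Items with N/A (Appendix 4).** Dryness, foreplay, masturbation, oral sex, intercourse: 5 of 7, of which 4 are pain items.

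**2. What a pain item measures.** Yes/all events = (pain risk when the activity occurs) × (share of events with the activity).

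- Pain constant at 80%, share 80% to 40%: 0.8 × 0.8 = 64%; 0.8 × 0.4 = 32%.
- Pain constant at 80%, share 70% to 60%: 0.8 × 0.7 = 56%; 0.8 × 0.6 = 48%.
- Pain halved from 80% to 40%, share 40% to 80%: 0.8 × 0.4 = 32%; 0.4 × 0.8 = 32%.

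In the first two cases yes/(yes+no) stays at 80%. In the third it shows the fall from 80% to 40%.

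**3. Dryness item.** Applicable in 90% of events and less dry in half: 0.9 × 0.5 = 45%. Applicable in 50% and less dry in 90%: 0.5 × 0.9 = 45%. The gain is hidden.

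**4. SAP read as any pain in an event.** Assume other pain in 20% of events without intercourse pain. Any pain = 1 − (1 − risk × share)(1 − 0.2). Share 80%: 1 − 0.36 × 0.8 = 71%. Share 40%: 1 − 0.68 × 0.8 = 46%. N/A misclassifies no event here, but the figure still moves with activity mix.

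**5. Illustrative test behaviour, only if the SAP test is run per item.** The simulation used 10 women (Protocol 8.1) and events per period Poisson with mean 6, capped at 10 (10 forms on Day 0, Section 5.4; the same number assumed later). Share s and risk p vary between women as Beta(8s, 8(1−s)) and Beta(8p, 8(1−p)), with within-woman correlation 0, 0.5 or 0.9 between periods. The test was the exact signed-rank test at two-sided 0.05, with 4,000 trials per scenario. Entries are the percentage of trials with a significant fall, as a range over the three correlations.

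| Share; pain risk | yes/all events | yes/(yes+no) |
|---|---|---|
| 80% to 40%; 80% throughout | 66–80% | under 1% |
| 80% to 60%; 80% throughout | 21–29% | 1% |
| 70% to 60%; 80% throughout | 7–9% | 1–2% |
| 40% to 80%; 80% to 40% | 2% | 56–66% |
| 50% to 70%; 80% to 40% | 15–18% | 61–71% |
| 60% stable; 80% to 40% | 46–56% | 63–72% |

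With nothing changing (share 60%, risk 80%), two-sided rejection is 5% against 2–3%. With a mean of 4 events, a stable 60% share and correlation 0, detection of a halving is 32% against 37%, so the gain is then small.

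**6. Selective avoidance.** The simulation draws share and risk independently. Suppose instead that latent risk stays at 80% and a would-be-painful occasion has 10 times lower odds of taking place. Let a and b be the probabilities that a painful and a painless occasion takes place, so 0.8a + 0.2b = share, and the conditional figure is 0.8a/share. Share 80%: a = 0.758, giving 76%. Share 40%: a = 0.298, giving 60%. Significant falls are then about 7% for yes/(yes+no) and about 70% for all events (2,000 runs, correlation 0).

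**7. Recording period.** With ±7-day windows the last interval runs from 133 − 119 = 14 to 147 − 105 = 42 days. If pain is 80% for the first 14 of 42 days and 40% for the last 28, with events evenly spread, the whole interval gives (14 × 80 + 28 × 40)/42 = 53%, against 40% for the last four weeks.

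**8. Week 0.** Even if forms were handed out at screening, they would cover 0 to 28 days before Day 0 (Sections 5.2 and 5.4), reaching four weeks only at the limit of the window.

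**The case against.** The strongest reply is that the all-events percentage is a legitimate choice of target. The share of a woman's sexual events that hurt is an interpretable measure of burden, and a fall in it is false only if one wanted pain given the activity. That stands, and is why the figure should be kept. It does not justify offering it as the only figure under a question about pain during a named activity.

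The reply can go further: the conditional percentage is not clean either. It selects on activity, and step 6 shows it falling from 76% to 60% when painful occasions are preferentially avoided. That also stands. It is much less affected than the all-events figure, but not immune.

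Third, the large rates in step 5 need a large shift in share; at 70% to 60% the rate is 7–9%. They also combine the protocol's per-item statistic with the SAP's test, a pairing neither document clearly specifies. So they illustrate direction and do not forecast this trial.

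Finally, the diary is unvalidated by the SAP's own account, secondary (Protocol Section 2), and used in a pilot of 10. This limits the stakes to the diary claims.

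**Conclusion.** The point holds for Protocol 8.3. Its rule is explicit, it covers every item, and it conflicts with the N/A options on the form. The distortion runs both ways. Its mechanism is arithmetic; its size is unknown, because N/A frequency is not given and every share and risk above is assumed.

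Three stronger readings are tempting, and the documents do not support them:

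- *The SAP has the same fault outright.* It does so only if its pain percentage is per item. Read as any pain, N/A misclassifies nothing, though activity mix still matters (71% to 46% in step 4).
- *There are no pre-treatment diary data.* The SAP says baseline diary data were collected. The protocol schedules none. That is a conflict between documents, not evidence that the data are absent.
- *The difference between four weeks and the time since the previous visit touches counts only.* That needs pain to be constant over the interval. If pain is changing, the percentage changes too (53% against 40% in step 7).

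The denominator and the undefined terms should be corrected, and the baseline conflict resolved, before any diary result is interpreted.

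**What to change.** **Denominator (Protocol 8.3 and SAP).** For the five items with N/A, make yes/(yes+no) the main percentage. Show the number of applicable events and of contributing women at each visit, and keep yes/all events as a supporting row. Keep total events as the denominator for lubricant use and stopping early.

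**SAP terms.** State whether the pain percentage is per item or any pain in an event, and which diary answer counts as lubrication difficulty.

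**Baseline.** Reconcile Protocol 5.2, 5.4, 5.5 and Appendix 1 with the SAP's diary paragraph. If no pre-dose diary exists, use the first collected diary (Visit 3) as the reference and label it on-treatment.

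**Period.** Choose one recording period for both documents, and report event counts per 28 days of actual diary time.

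**Cost.** The denominator change needs one definition in each document and one extra row. N/A is already on the form, but it must be confirmed that it was stored apart from No. Women with no applicable event drop out of that item: in the simulations, 8.5 to 9.5 of 10 intercourse pairs remain at a mean of 6 events and 7.2 to 8.4 at a mean of 4, with fewer for rarer activities. Because the conditional figure is open to selective avoidance, both figures should be read together. The baseline point may cost more: a missing pre-dose diary cannot be rebuilt, and the comparison would then have to be relabelled.
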